9.8.6 Vision Symptom Questionnaire

Post-Amendment 3, patients/caregivers will be asked to complete a Vision Symptom Questionnaire at Visits B, C, D, E, and F (Appendix 6). The questionnaire will ask patients/caregivers to describe any visual impairment or eye conditions for the patient.

Adverse events of vision disorders and/or symptoms detected on the Vision Symptom Questionnaire will be reported on the Adverse Event Form. The severity of the event and the relationship to the study drug will be assessed by the investigator and reported on the Adverse Event Form.

If a patient < 8 years old has started treatment and develops visual or ophthalmologic symptoms (ie, blurry vision, dry eye, dilated pupils, constant squinting, eyes drifting outward) it will be recommended that the patient is referred to a pediatric ophthalmologist for a comprehensive eye examination.

9.9 Appropriateness of Measurements

Urinary diaries are non-invasive tools that provide a record of bladder function in neurogenic and non-neurogenic conditions. The data collected from these diaries give an indication of urinary patterns and severity of symptoms. The urinary diary can be used effectively to assess improvement of urinary incontinence during treatment and is an appropriate tool to use in this study.

Urodynamic measurements are the gold standard for evaluating bladder and sphincter function and for documenting the effectiveness of new drugs and treatment paradigms. Urodynamic data can provide supporting evidence of changes in bladder function following treatment with anticholinergics.

The safety assessments, including adverse events review, physical examination, vital signs, and laboratory evaluations represent standard evaluations in clinical studies evaluating anticholinergic agents. The assessment of skin erythema at the local application site is useful in determining the irritation potential of transdermal applications, like the oxybutynin topical gel.

The sparse blood sampling methodology is appropriate for this pediatric study, to minimize the amount of blood sampling and for the determination of average oxybutynin and N-desethyloxybutynin plasma concentrations.

10 QUALITY CONTROL AND ASSURANCE

The sponsor will implement and maintain quality control procedures to ensure that this study is conducted, and data are generated, documented, and reported in compliance with the protocol, GCP, and applicable regulatory requirements.

The sponsor or designee will routinely conduct monitoring and/or auditing visits to the study centers to verify the adherence to the study protocol, the protection of the rights and well- being of the *patients*, and the accuracy and completeness of reported study data recorded on the source documentation.

11 PLANNED STATISTICAL METHODS

11.1 Determination of Sample Size

Sample size was calculated for the protocol as originally designed (Pre-Amendment 3: doubleblind, placebo-controlled treatment period followed by an open-label extension) as follows:

This study *was planned to* include a minimum of 96 pediatric *patients* aged 6 to < 17 years who have a diagnosis of detrusor overactivity associated with a neurological condition. The sample size was selected to provide an adequate number of *patients* to evaluate the safety and efficacy of *oxybutynin chloride gel* treatment in a pediatric population. *Patients were* randomized in a 1:1 fashion to *oxybutynin chloride gel* or placebo within each stratification level, which *were* based on age, weight, and gender. Estimates for the average change from baseline (CFB) in the percentage of catheterizations without a leaking accident as well as the standard deviation for this variable *were* taken from oxybutynin TDS in Study O03010. Assuming a common standard deviation of 28 for the CFB in the percentage of catheterizations without a leaking average for *oxybutynin chloride gel* = 25 and average for placebo = 5), and n = 48 *patients* per treatment group, and then there is 93% power to detect a statistically significant difference between treatment groups. Based on discontinuation rates from Study O03010, if we assume a 10% dropout rate then there is 90% power to detect a statistically significant difference between treatment groups.

The open-label study (patients enrolled Post-Amendment 3) will include a minimum of 25 pediatric patients aged 3 to < 17 years (efforts will be made to enroll a greater number of patients aged 3 years to < 6 years) who have a diagnosis of detrusor overactivity associated with a neurological condition. This sample size is expected to provide a minimum of 10 patients with 14 weeks of exposure.

11.2 Analysis Populations and Databases

Statistical analysis and data tabulation will be performed using *data from the open-label period for patients enrolled after Amendment 3 and the data from the double-blind and open-label periods for patients enrolled prior to Amendment 3 in* the following patient populations unless specified otherwise:

- Safety populations:
 - Post-Amendment 3 open-label safety population
 - Pre-Amendment 3 double-blind safety population
 - Pre-Amendment 3 open-label safety population
 - Combined open-label safety population (Pre- and Post-Amendment 3)
- Intent-to-treat (ITT) populations:
 - Combined ITT population (Pre- and Post-Amendment 3; primary efficacy analysis population)
 - Post-Amendment 3 ITT population
 - Pre-Amendment 3 ITT population

- Per-protocol (PP) populations:
 - Post-Amendment 3 PP population
 - Pre-Amendment 3 PP population
- PK populations:
 - Post-Amendment 3 PK population
 - Pre-Amendment 3 PK population
 - Combined PK population (Pre- and Post-Amendment 3)

The *Post-Amendment 3 open-label* safety population is defined as all *patients* who receive at least *1* dose of *study treatment in* the open-label period *after Amendment 3*.

The Pre-Amendment 3 double-blind safety population is defined as all patients who receive at least 1 dose of study treatment in the double-blind period before Amendment 3.

The Pre-Amendment 3 open-label safety population is defined as all patients who receive at least 1 dose of study treatment in the open-label period before Amendment 3.

The combined open-label safety population is defined as all patients who receive at least 1 dose of study treatment in the open-label period before or after Amendment 3.

The primary efficacy analysis populations will be the *Post-Amendment 3* ITT population *and the Pre-Amendment 3 ITT population*.

The combined ITT population will include all patients who have a baseline value for the primary efficacy variable in the Post-Amendment 3 open-label period or all randomized patients who have a baseline value for the primary efficacy variable in the Pre-Amendment 3 double-blind period.

The Post-Amendment 3 ITT population will include all randomized patients who have a baseline value for the primary efficacy variable in the Post-Amendment 3 open-label period.

The *Pre-Amendment 3* ITT population will include all randomized patients who have a baseline value for the primary efficacy variable *in the Pre-Amendment 3 double-blind period*.

The *Pre-Amendment 3* PP population will include all *patients* in the *Pre-Amendment 3* ITT population who complete the *double-blind* treatment period of the study and who are without significant protocol violations.

The Post-Amendment 3 PP population will include all patients in the Post-Amendment 3 ITT population who complete the Post-Amendment 3 open-label treatment period of the study and who are without significant protocol violations.

The PK population will include all *patients* who have at least 1 sample draw for plasma concentrations. The PK population will only be used in the summary statistics and analyses of the *PK* data.

Additionally, 2 types of visits are defined for the purposes of analysis and summary:

- Observed cases (OC)
- Last observation carried forward (LOCF)

The OC visits are defined to be those assessment values observed at each scheduled visit. All applicable efficacy and safety variables will be summarized using the OC visits.

The LOCF visit is defined as the last data recorded for each efficacy variable. This visit will be *designated as* Week 6 (LOCF). *The Week 6 (LOCF) visit will be defined for the Post-Amendment 3 open-label period and the Pre-Amendment 3 double-blind period* and will only be used to summarize efficacy data. The LOCF visit provides missing value imputation for *patients* who do not complete the *open-label treatment period (Post-Amendment 3) or the double-blind treatment period (Pre-Amendment 3)* of the study and will include all *patients* in the *corresponding* ITT population.

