- Detrusor pressures at maximum bladder capacity
- Maximum amplitude of involuntary detrusor contractions
- Volume at first involuntary detrusor contraction
- Presence (versus total absence) of involuntary detrusor contractions at > 15 cm H20

Safety Assessments:

Safety will be evaluated by monitoring adverse events, physical examinations, vital signs, and clinical laboratory evaluations including hematology, serum chemistries and urinalysis, assessing for local skin erythema at the application site, and visual assessments. The investigator will assess vital signs, adverse events, skin erythema, complete the anticholinergic questionnaire, and the vision symptom assessment questionnaire. Analyses and summaries will be performed under the Pre-Amendment 3 double-blind phase, the Pre-Amendment 3 open-label phase, and the Post-Amendment 3 open-label phase, with groups aggregated where appropriate.

Other Evaluations:

Statistical Methods:

All efficacy, safety, and other evaluation data will be summarized using descriptive statistics for continuous variables and frequency distributions for categorical variables.

The primary endpoint analysis will compare the difference between oxybutynin chloride gel (combined from Pre-Amendment 3 and Post-Amendment 3) and placebo in the change from baseline in the percentage of catheterizations without a leaking accident at Week 6 (LOCF) for the intent-to-treat (ITT) population using an analysis of covariance model with the baseline measure of the primary variable as the covariate and treatment group as factor. Analyses for secondary endpoints will use similar analysis of covariance models to compare differences between the treatment groups for the change from baseline to Week 6 (LOCF) for the ITT population.

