11.5.1 Statistical Analysis of the Primary Efficacy Endpoint

The primary efficacy *parameter is the CFB to Week 6 (or LOCF) in the percentage of catheterizations without a leaking accident. The primary efficacy parameter* will be analyzed using an analysis of covariance (ANCOVA) model with the baseline measure of the primary variable as the covariate and treatment group *and study part (Pre-Amendment 3 and Post-Amendment 3) as factors.*

To assess the effect of the study design, the primary efficacy parameter will be analyzed using a random effects mixed model using the combined data from the Pre-Amendment 3 doubleblind treatment period and the data from the Post-Amendment 3 open-label treatment period. The model will include the baseline measure and other baseline characteristics as covariates and treatment (Pre-Amendment 3 double-blind placebo, Pre-Amendment 3 double-blind oxybutynin chloride gel, Post-Amendment 3 open-label oxybutynin chloride gel) as factors and will account for the heterogeneity between parts of the study (Pre-Amendment 3 vs Post-Amendment 3) by using a random effect for study part. If the analyses indicate heterogeneity, the data from the Pre-Amendment 3 double-blind treatment period and the data from the Post-Amendment 3 open-label treatment period will be analyzed separately. For the Post-Amendment 3 ITT population, the significance of the change from baseline on the primary efficacy measure will be assessed from a 2-sided, 1-sample t-test. For the Pre-Amendment 3 ITT population the primary efficacy parameter will be analyzed using an ANCOVA model with the baseline measure of the primary variable as the covariate and treatment group as factors.

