5.2.2 Changes to Analyses Prior to Database Lock

Version	Date	Summary
1.0	24 Oct 2017	Original version
2.0	28 Mar 2022	 Exact (Clopper-Pearson) 95% CI, Exact unconditional 95% CI using the score statistic, and Cochran-Mantel-Haenszel (CMH) was added in Table 5-2 to analyze binary urodynamic variable (Presence (versus total absence) of involuntary detrusor contractions at > 15 cm H2O)
		 CFB Mixed Model was deleted from Table 5-2. All CFB Mixed model analyses have been replaced with CFB ANCOVA as reflected in Table 5-12
		 Study part was removed as a factor from the CFB ANCOVA models
		 Details of how urodynamic assessments will be analyzed have been added in Table 5-12
		 Section 5.1.1.2 was modified to clarify analysis populations presented in demographics tables.
		 Exact Kolmogorov-Smirnov test was added in Table 5-2 to compare whether distributions of efficacy endpoints between patients treated with oxybutynin chloride gel in the two parts (Pre-Amendment 3 and Post-Amendment 3) of the study are the same
		 Section 5.1.1.3.1 was modified to provide details on how efficacy endpoints will be analyzed based on whether the distributions of efficacy endpoints between patients treated with oxybutynin chloride gel in the two parts (Pre- Amendment 3 and Post-Amendment 3) of the study were the same or not
		 Updated Table 5-15 definition of treatment-emergent adverse events in double-blind period to distinguish between participants who enter the 8-week open-label period from those that do not

6. Data Handling and Analysis Conventions

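### Protocol Amendment 4 contradicts itself and SAP v2.0 on the primary efficacy analysis, and the candidate analyses estimate different gel-versus-placebo contrasts

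*Protocol*

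**What the plan says.** Protocol Amendment 4 (dated 31 October 2022) designates the primary analysis in three places.

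- **Population, 11.2.** The list of populations has the "Combined ITT population (Pre- and Post-Amendment 3; primary efficacy analysis population". Further down the same section: "The primary efficacy analysis populations will be the *Post-Amendment 3* ITT population *and the Pre-Amendment 3 ITT population".
- **Model, Synopsis (Statistical Methods).** The primary analysis "will compare the difference between oxybutynin chloride gel (combined from Pre-Amendment 3 and Post-Amendment 3) and placebo", "using an analysis of covariance model with the baseline measure of the primary variable as the covariate and treatment group as factor". There is no study-part term.
- **Model, 11.5.1.** The ANCOVA has treatment group "and study part (Pre-Amendment 3 and Post-Amendment 3) as factors". A mixed model follows that "will account for the heterogeneity between parts of the study (Pre-Amendment 3 vs Post-Amendment 3) by using a random effect for study part". If heterogeneity is found, the parts are analysed separately: an ANCOVA for Pre-Amendment 3 and a one-sample t-test for Post-Amendment 3. No criterion for heterogeneity is given.

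SAP 5.1.1.3.1 has another rule. An exact two-sample K-S test compares the primary endpoint between Pre- and Post-Amendment 3 gel patients. At p ≥ 0.05 the primary analysis is the Combined ITT ANCOVA with baseline and treatment only. At p < 0.05 the parts are analysed separately. The method not selected becomes supplementary. The SAP 5.2.2 entry for version 2.0 (28 Mar 2022) says "Study part was removed as a factor from the CFB ANCOVA models" and also records deletion of the mixed model.

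**The concern.** A confirmatory result needs one contrast, named in advance and the same wherever it is described. Here the protocol's two population designations differ, its two models differ, and the SAP uses a selection rule found nowhere in the protocol. The SAP log would settle this if the protocol had then been brought into line. Instead, the amendment dated seven months later still carries both the study-part factor and the mixed model.

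This goes beyond wording. One candidate rests on the randomised, blinded comparison. The other adds open-label gel patients, recruited later and from age 3 rather than 6, to one side of a comparison with blinded placebo. The endpoint is a diary kept by patient or caregiver, so an open-label shift is plausible. A result near the threshold could be positive under one description of the primary analysis and negative under another.

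**Working it through.** **Inputs.** From Protocol 11.1 and SAP 5.1.2: SD 28, planned means 25 (gel) and 5 (placebo), 48 per arm, 10% dropout, and at least 25 Post-Amendment 3 patients, all on gel. Assumed: two-sided 0.05 (neither document states an alpha for the primary test); 20, 30 or 48 Pre-Amendment 3 patients per arm (actual enrolment is not given); a baseline unrelated to the change. *Shift* means the Post gel mean minus the Pre gel mean.

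**Step 1. The plan's own figure.** The noncentrality is 20 / (28 × √(2/48)) = 20 / 5.72 = 3.50, which gives power 0.934 (stated: 93%). With 48 × 0.9 ≈ 43 per arm it is 0.906 (stated: 90%). Both are reproduced. They apply only to the randomised contrast; neither document gives power for the combined analysis.

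**Step 2. What each model estimates.** There are three cells: Pre placebo (P), Pre gel (G1, n patients) and Post gel (G2, 25 patients).

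- With study part, the Post cell has its own parameter. The treatment coefficient is G1 − P, the randomised contrast. Post patients inform only the baseline slope and the residual variance.
- Without study part, the coefficient, apart from baseline adjustment, is (n·G1 + 25·G2)/(n + 25) − P = (G1 − P) + [25/(n + 25)] × (G2 − G1).

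The weight on the shift is 25/45 = 0.56 at n = 20, 25/55 = 0.45 at n = 30 and 25/73 = 0.34 at n = 48.

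The 11.5.1 mixed model cannot measure heterogeneity separately. Its three-level treatment factor already distinguishes Post from Pre, so the random part effect is confounded with it.

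**Step 3. Same data, two answers.** Observed means are in the order P / G1 / G2.

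| Means | n per arm | Without study part | With study part |
|---|---|---|---|
| 5 / 15 / 25 | 48 | 10 + 0.342 × 10 = 13.4, SE 5.23, p = 0.012 | 10.0, SE 5.72, p = 0.083 |
| 5 / 15 / 25 | 20 | 10 + 0.556 × 10 = 15.6, SE 7.55, p = 0.044 | 10.0, SE 8.85, p = 0.26 |
| 5 / 25 / 5 | 20 | 20 − 0.556 × 20 = 8.9, SE 7.80, p = 0.26 | 20.0, SE 8.85, p = 0.027 |

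The third row shows that pooling can also hide a randomised effect.

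**Step 4. How often (simulation, 4,000 trials per scenario, both models fitted to the same data).**

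| True effect | Shift | Result over 20 to 48 per arm |
|---|---|---|
| 20 (planned) | 0 | models disagree on significance in about 4-19% of trials, least at 48 per arm |
| 10 | 0 | disagree in about 14-15% |
| 10 | 10 | disagree in about 30-33%; significant in about 50/60/72% without study part and 20/28/41% with it (20/30/48 per arm) |
| 0 | 20 | significant in about 24-29% without study part, about 5% with it |

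For the last row, if the SAP rule is applied first, the K-S test selects the pooled analysis and that analysis is significant for gel in about 14/12/7% of trials (20/30/48 per arm).

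**The case against.** The strongest reply is that the SAP governs. SAP 5.1 says that it expands the protocol's statistical section, 5.2 says that it details changes from it, and 5.1.1.3.1 gives a definite rule. The Synopsis matches the SAP's pooled branch, so 11.5.1 may simply be uncorrected text. The pooled and separate branches could also account for the two designations in 11.2. This has force, and it rules out three stronger readings that a reader might infer.

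- **That no primary analysis is pre-specified.** The SAP does specify one, conditional on the K-S test.
- **That the analysis can be picked once results are known.** Protocol 9.4.5 keeps the double-blind part blinded during Post-Amendment 3, and SAP 5.1 requires approval before database lock. That the data have been collected does not show that treatment results are available.
- **That the trial runs a 24-29% false-positive risk.** That figure leaves out the K-S rule and needs an open-label shift as large as the planned effect.

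It is also fair that an effect of 10 is half the planned value, and that with no shift the disagreement reflects additional gel patients and sampling noise rather than bias.

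The reply does not remove the conflict. The protocol amendment postdates the SAP version and keeps what that version deleted. The dates alone do not show whether Amendment 4 meant to reaffirm the study-part model or failed to update it. The K-S rule also still allows the unrandomised contrast to be primary, and its separate branch has two tests with no statement of how they combine.

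**Conclusion.** The point holds as a conflict between the current protocol's own statements, and between that protocol and SAP v2.0, about which contrast is primary. It should be fixed before database lock. The textual conflict rests on no assumption; its numerical consequence does. Disagreement between the two protocol models is modest at the planned effect with full enrolment and no shift (about 4%). It rises to about 19% at 20 per arm, and to about a third if the effect is half the planned size and the open-label shift equals it. Disagreement here means significant versus not significant at an assumed two-sided 0.05. With an inert gel and a shift of 20, the SAP rule lowers the pooled model's false-positive rate from 24-29% to about 7-14%, which is still above the roughly 5% of the randomised contrast.

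**What to change.** State one gel-versus-placebo primary contrast identically in the Synopsis, Protocol 11.2, Protocol 11.5.1 and SAP 5.1.1.3.1: Pre-Amendment 3 ITT, change from baseline to Week 6 (LOCF), ANCOVA with baseline and treatment group, two-sided 0.05. This matches the Pre-Amendment 3 primary objective in Protocol 8.1, and both documents already plan the model.

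- In 11.2, change both the primary tag on the Combined ITT line and the later sentence naming the Post and Pre ITT populations.
- Use one definition of the Pre-Amendment 3 ITT. Protocol 11.2 requires a baseline value; SAP Table 5-1 requires a post-baseline value.
- Keep the Post-Amendment 3 one-sample test as the separate analysis of the Post-Amendment 3 objective, and say that it is not evidence against placebo.
- Label the pooled models, with and without study part, as supportive.

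The cost is that open-label patients leave the deciding test. For a difference of 20 and SD 28, power is about 93% at 48 per arm. At 30 per arm it is about 77-78% (noncentrality 20/7.23 = 2.77), and at 20 per arm about 58-60% (20/8.85 = 2.26). The documents do not give actual Pre-Amendment 3 enrolment, so the revised text should state power for that number. No new data or new models are needed.

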11.3 Efficacy Parameters

The primary efficacy variable *for the Post-Amendment 3 open-label period and the Pre-Amendment 3 double-blind period* will be the percentage of catheterizations without a leaking accident (continuous variable).

The following are secondary continuous efficacy variables that will be calculated:

- Average volume of urine collected per catheterization (for *Pre-Amendment 3 population* only)
- Average volume of urine collected *at first* (morning awakening) catheterization
- Average number of catheterizations per day

The primary efficacy endpoint *for the Post-Amendment 3 open-label period and the Pre-Amendment 3 double-blind period* is defined as the CFB to Week 6 (LOCF) in the percentage of catheterizations without a leaking accident. The secondary efficacy endpoints are defined as the CFB in the secondary efficacy variables at Week 6 (LOCF).

Baseline is Visit 2 for Pre-Amendment 3, and baseline is Visit B for Post-Amendment 3.

